### **Length of Study**

The total length of the study, from screening of the first patient to the end of the study, is expected to be approximately 9 years.

The randomized treatment phase will continue for 24 weeks (includes a 16-week treatment period and an 8-week safety follow-up period) after the last patient is enrolled into the study or until the sponsor decides to terminate the study, whichever is earlier. Patients who withdraw from the treatment period should complete the 8-week safety follow-up period. All patients will be offered participation in the 104-week extended PML monitoring phase.

The OLE phase will continue for approximately 6 years after the last patient is enrolled into the study or until the Sponsor decides to terminate the study, whichever is earlier.

The PML monitoring phase will last 104 weeks for patients who enter, either from the randomized treatment phase or the OLE phase (*includes 12-week safety follow-up period after completion or early discontinuation from OLE*).

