##### **4.4.2.2      Rescue Therapies**

The worsening of UC or CD may result in the use of rescue medications, based on the discretion of the Principal investigator.

At any time during the study, patients who have worsening of their UC or CD will be permitted to receive additional therapy with steroids (IV, oral, or topical). Addition of or increases in doses of 5-ASA (oral or topical) and/or immunosuppressants (i.e., AZA, 6-MP, or MTX) will also be allowed if clinically indicated by the Principal Investigator.

Rescue therapy with anti-TNF agents or their corresponding biosimilars, cyclosporine, tacrolimus, sirolimus, MMF, anti-adhesion molecules, natalizumab, vedolizumab, ustekinumab, efalizumab, rituximab, other lymphocyte depleting agents (except AZA and 6-MP), or other biological or investigational therapeutics will not be allowed in conjunction with etrolizumab because of the level of immunosuppression anticipated with the use of these agents. Patients who receive such therapies are not to receive further study treatment or enter the open-label treatment phase, and will be required to enter safety follow-up period. All patients will be offered participation in the 104-week PML monitoring phase (*includes 12-week safety follow-up period after completion or early discontinuation from OLE*).

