#### **Safety Follow-up Period Assessments**

Safety follow-up will be conducted for a period of 8 weeks. Patients will be assessed for the safety follow-up period at intervals specified in [Appendix 1b](#). The visits should be scheduled based on the date of the last dose in the treatment phase.

Following the safety follow-up period, patients will have the option to continue into the OLE phase. If the patient chooses not to continue to receive etrolizumab treatment in the OLE phase, they will be offered participation in the 104-week PML monitoring phase (*includes 12-week safety follow up period after completion or early discontinuation from OLE*) as specified in [Appendix 1e](#). Patients will participate in telephone assessments every 6 months to assess emergence of symptoms and signs of PML. In total, follow-up for the development of any signs or symptoms of PML will be conducted for a period of 2 years after last dose of study drug.

Patients who discontinue from the study prior to completion of the safety follow-up phase will be asked to return to the clinic within 30 days ( $\pm 7$  days) after the last dose of study drug or last scheduled visit for an early termination visit.

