### **4.6 TREATMENT, PATIENT, STUDY, AND SITE DISCONTINUATION**

#### **4.6.1 Study Treatment Discontinuation**

Patients must permanently discontinue study treatment if they experience any of the following:

- Any medical condition that the investigator or Sponsor determines may jeopardize the patient's safety if he or she continues to receive study treatment
- Investigator or Sponsor determines it is in the best interest of the patient
- Pregnancy
- Anaphylaxis or other severe hypersensitivity reaction
- Develop colonic mucosal dysplasia
- Malignancy (with the exception of local and resected basal or squamous cell carcinoma of the skin) or cervical Pap test with AIS, HSIL, or CIN of Grade >1

- Specific serious infection (see Section 5.1.1.1 for details on serious infection):
  - Any patient who experiences a specific de novo or reactivated serious viral infection, such as HBV, HCV, HIV, should discontinue study medication.
  - Any patient who develops life-threatening infections during the study should discontinue study medication.

The primary reason for study treatment discontinuation should be documented on the appropriate eCRF.

Patients will return to the clinic for an early withdrawal from treatment or treatment discontinuation visit after the last dose of study drug (see [Appendix 1](#) for additional details).

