#### **Education, Monitoring, and Management**

After each injection administered in the treatment phase and after the first four injections in the OLE phase, the patient must be monitored for 60 minutes for any possible hypersensitivity reaction. Medicinal products for the treatment of hypersensitivity reactions (e.g., epinephrine, antihistamines, and glucocorticoids) must be available for immediate use in the clinic for the event of an allergic reaction during administration of the study drug. Resuscitation equipment should also be available.

Patients and their caregivers should be instructed to recognize the symptoms of any anaphylactic, anaphylactoid, or hypersensitivity reaction and to contact a health care provider (HCP) or seek immediate care in case of any such symptoms. Patients are to be provided with alert cards to remind them and a caregiver or partner of the above. Please see [Appendix 9](#) for diagnosing anaphylaxis.

Patients with symptoms of anaphylaxis or with severe hypersensitivity reactions (e.g., stridor, angioedema, life-threatening change in vital signs) must be permanently withdrawn from study drug treatment. These patients will not be eligible to receive open-label etrolizumab but are required to enter the safety follow-up phase, and offered participation in the PML monitoring phase.

All adverse events of systemic hypersensitivity reactions or anaphylactoid or anaphylaxis reactions must be reported within 24 hours to the Sponsor and the Medical Monitor must be informed as soon as is practical (see the Study Manual for contact information).

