### **5.3.1 Adverse Event Reporting Period**

Investigators will seek information on adverse events at each patient contact.

All adverse events, whether reported by the patient or noted by study personnel, will be recorded in the patient's medical record and on the Adverse Event eCRF.

After informed consent has been obtained but prior to initiation of study drug, only serious adverse events caused by a protocol-mandated intervention (e.g., invasive procedures such as biopsies, discontinuation of medications) should be reported (see [Section 5.4.2](#) for instructions for reporting serious adverse events).

After initiation of study drug, all adverse events will be reported regardless of relationship to study drug, up until the patient completes his or her last study visit (in the Safety Follow-Up Phase) or 12-weeks after the last study drug administration whichever is longer. After the Safety Follow-Up Phase, the investigator should report any serious adverse events that are believed to be related to prior study drug treatment (see [Section 5.6](#)). In addition, the Sponsor should be notified if the investigator becomes aware of any post-study events of confirmed or suspected PML, regardless of relationship to study drug, for up to 2 years after the patient's last dose of study drug (see [Section 5.6](#)).

Instructions for reporting adverse events that occur after the adverse event reporting period are provided in [Section 5.6](#).

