##### **5.4.2.2 Events That Occur after Study Drug Initiation**

After initiation of study drug, serious adverse events and adverse events of special interest will be reported until 12 weeks after the last dose of study drug. Investigators should record all case details that can be gathered immediately (i.e., within 24 hours after learning of the event) on the Adverse Event eCRF and submit the report via the electronic data capture (EDC) system. A report will be generated and sent to Safety Risk Management by the EDC system.

In the event that the EDC system is unavailable, the paper Clinical Trial Serious Adverse Event/Adverse Event of Special Interest Reporting Form provided to investigators should be completed and submitted to the Sponsor or its designee immediately (i.e., no more than 24 hours after learning of the event), either by faxing or by scanning and emailing the form using the fax number or email address provided to investigators. Once the EDC system is available, all information will need to be entered and submitted via the EDC system.

Instructions for reporting serious adverse events that occur more than 12 weeks after the last dose of study treatment are provided in Section [5.6](#).

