## **5.6 ADVERSE EVENTS THAT OCCUR AFTER THE ADVERSE EVENT REPORTING PERIOD**

The Sponsor should be notified if the investigator becomes aware of any serious adverse event that occurs after the end of the adverse event reporting period (defined as 12 weeks after the last dose of study drug, see Section 5.3.1) if the event is believed to be related to prior study drug treatment. In addition, the Sponsor should be notified if the investigator becomes aware of any post-study events of confirmed or suspected

progressive multifocal leukoencephalopathy, regardless of relationship to study drug, for up to 2 years after the patient's last dose of study drug. These events should be reported through use of the Adverse Event eCRF. However, if the EDC system is not available, the investigator should report these events directly to the Sponsor or its designee, either by faxing or by scanning and emailing the paper Clinical Trial Serious Adverse Event/Adverse Event of Special Interest Reporting Form using the fax number or email address provided to investigators.

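### Patients who stop randomized treatment early but stay in the study have an 8-week follow-up against a 12-week adverse event window, so Weeks 8 to 12 after the last dose can pass with no scheduled contact.

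*Combined protocol and SAP*

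**What the plan says.** **Follow-up length.** The synopsis and Section 3.2 give the same rule for early stoppers: "Patients who withdraw from the treatment period should complete the 8-week safety follow-up period". Section 4.5 sets the anchor: "The visits should be scheduled based on the date of the last dose in the treatment phase". Appendix 1b lists three follow-up visits, labelled Weeks 18, 20 and 24 (Days 126, 140 and 168), and none later. It gives no offsets for a patient who stopped early. Section 4.6.1 adds a visit on stopping, with no timing in the text: "Patients will return to the clinic for an early withdrawal from treatment or treatment discontinuation visit after the last dose of study drug".

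**Reporting window.** Section 5.3.1 runs reporting of all adverse events to the last follow-up visit or "12-weeks after the last study drug administration whichever is longer". Section 5.4.2.2 says "serious adverse events and adverse events of special interest will be reported until 12 weeks after the last dose of study drug". Section 5.6 describes the reporting period as "defined as 12 weeks after the last dose of study drug".

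**Who must be followed.** Patients withdrawn for anaphylaxis or severe hypersensitivity "are required to enter the safety follow-up phase, and offered participation in the PML monitoring phase" (Section 5.1.1.2, Hypersensitivity Reactions). Patients given excluded rescue therapy "are not to receive further study treatment or enter the open-label treatment phase, and will be required to enter safety follow-up period" (Section 4.4.2.2).

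**What comes next.** The first scheduled PML call is 24 weeks after stopping treatment (Appendix 1e). Footnote j to that appendix relieves investigators of active adverse event monitoring in that phase.

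**The concern.** Section 5.3.1 links questioning about adverse events to contact with the patient. Where no contact is scheduled, the last part of the 12-week window depends on families or sites raising events unprompted.

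Completers in both arms are seen at 12 weeks or later after their last dose. Patients leaving the open-label extension have a 12-week follow-up under Appendix 1d. Only early stoppers in the randomized phase lack an assured contact at 12 weeks, so ascertainment could differ between them and everyone else.

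Infection-related adverse events are a listed safety endpoint (Table 1), and some of these patients will have just received immunosuppressive rescue agents. Patients who leave the study outright are a separate matter and are not part of this point.

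**Working it through.** This is calendar arithmetic. No power or sample-size figure is involved.

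**1. The plan's own figure: 104 weeks of PML monitoring (Appendix 1e).**
- Early stoppers, footnote e: 8 + 96 = 104.
- Completers, footnote c: 4 (Weeks 12 to 16) + 8 + 92 = 104. This fits the Q4W last dose at Week 12.

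Both sums reproduce the stated total. Section 4.5 describes that total as 2 years from the last dose. The completers' sum includes the 4 weeks between last dose and start of follow-up; the early stoppers' sum has no such term. This favours counting their 8 weeks from the last dose, though it does not prove it.

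**2. Completers, from the Appendix 1b days.**

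| Arm | Last dose | Day 126 | Day 140 | Day 168 |
|---|---|---|---|---|
| Q4W | Day 84 | 42 d = 6 wk | 56 d = 8 wk | 84 d = 12 wk |
| Q8W | Day 56 | 70 d = 10 wk | 84 d = 12 wk | 112 d = 16 wk |

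At nominal dates the last visit reaches 12 weeks in both arms, so the gap is 0.

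**3. Early stoppers.** Let d be the weeks from last dose to the start of the 8-week follow-up. Then gap = max(0, 12 − (d + 8)).

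| d (weeks) | 0 | 1 | 2 | 3 | 4 | 8 |
|---|---|---|---|---|---|---|
| Gap (weeks) | 4 | 3 | 2 | 1 | 0 | 0 |

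- Counted from the last dose, d = 0: 84 − 56 = 28 days, or 25 to 31 days with the ±3-day visit window. That is 4/12 = 33% of the reporting window.
- Counted from the decision to stop: a stop at the next dosing visit has d = 4 (Q4W) or d = 8 (Q8W), so the gap is 0. A patient stopped for an injection reaction has d near 0, so both counts give about 4 weeks.
- Completers' spacing kept (+6/+8/+12 or +10/+12/+16 weeks): gap 0.

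**4. Next scheduled contact.** With d = 0, the last visit is at Week 8 and the PML call at Week 24: 24 − 8 = 16 weeks between contacts. Only Weeks 8 to 12 of that interval lie inside the reporting window.

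**5. Drug remaining.** Section 1.3 gives an adult half-life of 13 to 15 days. Assuming first-order decline, the fraction left is 0.5^(t/half-life):
- 8 weeks (56 days): 5.0% at 13 days, 7.5% at 15 days.
- 12 weeks (84 days): 1.1% at 13 days, 2.1% at 15 days.

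The paediatric half-life is unknown; estimating it is one of the study's aims.

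**The case against.** The strongest case against is that no reporting rule is missing. The whichever-is-longer clause in Section 5.3.1 already covers a patient whose visits end before Week 12. Known events are followed to resolution (Section 5.5.1), unscheduled visits are allowed, and families hold alert cards. An event from Weeks 8 to 12 that a family mentions at the PML call is still reportable. All of this stands, and it limits the point to scheduled questioning about new events.

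The anchor is also not fixed. Keeping the completers' spacing from last dose is a natural way to apply Section 4.5. Keeping the printed study days also closes the gap: no dose is later than Day 84, and 168 − 84 = 84 days. Appendix 1e counts from discontinuation of treatment, which need not be the last dose. This stands too, and it is why the gap is a range that includes 0. It does not remove the point: sites can reasonably choose different readings, and for a patient stopped at an injection the choice between last dose and stop date makes no difference.

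Lastly, the primary endpoints are PK and PD, safety is summarised descriptively, and no test or decision rule is affected. Nor do the documents show any special hypersensitivity risk in Weeks 8 to 12. Both are fair, and they argue for a small remedy.

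**Conclusion.** The concern holds as a possible gap in scheduled ascertainment. Before 12 weeks after the last dose, 0 to 4 weeks at nominal dates (0 to 31 days with the visit window) can pass without a scheduled contact for early stoppers who stay in the study. The 4-week end follows if their 8 weeks run from the last dose, or if they stop at or near a dose. The 0 end follows if follow-up starts 4 or more weeks after the last dose, or if completers' spacing or the printed study days are kept.

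The effect on adverse event incidence cannot be estimated. It is probably small, given the low drug levels expected by 8 weeks if children resemble adults, and it concerns mainly non-serious events. With about 24 patients randomized 1:1, one patient's missed event moves an arm's incidence by 1/12, about 8 percentage points. That shows how sensitive the summaries are; it is not a prediction. Confidence is medium, because the text leaves the anchor open. The change is still worth making because it costs so little.

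**What to change.** 1. In Section 4.5 and a footnote to Appendix 1b, give early stoppers' follow-up visits in weeks after the last dose.
2. Add one telephone adverse event contact at 12 weeks after the last dose for patients who stop randomized treatment early, stay in the study, and have no scheduled adverse event contact at or after that time. PML calls do not count as such a contact.
3. Add a matching clause to the synopsis and Section 3.2.

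This closes the gap under every reading. The method is already in the protocol: Appendix 1d uses telephone contacts at Weeks 4 and 8 after the extension. The 8-week clinic follow-up, the 104-week PML total and Appendix 1e stay as they are.

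The cost is one call per early stopper at most. The documents give no early-stop rate; at an assumed 5% to 25% of about 24 patients, that is 24 × 0.05 = 1.2 to 24 × 0.25 = 6 calls in the whole study.

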### **Investigational Medicinal Products**

#### **Test Product (Investigational Drug)**

The investigational medicinal product (IMP) for this study is etrolizumab. All patients will receive etrolizumab one subcutaneous injection of 0.01 mL per kg of patient weight (1.5 mg/kg) Q4W or injection of 0.02 mL per kg of patient weight (3 mg/kg) Q8W.

### **Statistical Methods**

#### **Primary Analysis**

The primary analysis of the study will be performed when all the data from the randomized controlled part of the study are in the database and has been cleaned and verified.

#### **Determination of Sample Size**

A sample size of 12–16 patients has been considered sufficient in order to evaluate the PK and PD endpoints. No formal sample size and power calculations were performed.

#### **Pharmacokinetic Analyses**

The PK analysis population will consist of patients with sufficient data to enable estimation of key parameters such as AUC (area under the curve), Cmax (maximum concentration), Ctrough (trough concentration) and t1/2 (elimination half-life).

Non-compartmental analysis will be used to derive PK parameters including Cmax and Tmax after the first and final dose, t1/2, AUC within dosing interval (AUC84-112) and (AUC56-112) for 1.5 mg/kg Q4W and 3 mg/kg Q8W, respectively.

All PK parameters will be listed and summarized by descriptive summary statistics including means, geometric means, ranges, standard deviations, and coefficients of variation.

Individual and mean concentration versus time data will be tabulated and plotted by dose level.

PK data from this study may be combined with data from the adult study to perform a population PK analysis. Population typical value of PK parameters will be estimated for the entire study population, along with estimates of intra- and inter-patient variance and an estimate of random error. Individual patient parameter estimates will be computed using the post hoc analysis

procedure. A prospective analysis plan will be prepared, and the population PK analysis will be presented in a report separate from the Clinical Study Report of this study.

Additional exploratory PK/PD analyses or modeling may be conducted as appropriate.

### **Pharmacodynamic Analyses**

All PD parameters will be listed and summarized by descriptive summary statistics including means, standard deviations, medians, ranges, and coefficients of variation.

### **Safety Analyses**

The safety analysis population will consist of all patients who received at least one dose of study drug, with patients grouped according to dose regimen received.

Safety will be assessed through descriptive summaries of adverse events (including serious adverse events, malignancies, infections – in particular gastrointestinal infections, systemic hypersensitivity events, and injection site reactions), laboratory test results, and vital signs.

### **Immunogenicity Analyses**

The immunogenicity analysis population will consist of all patients with at least one anti-drug antibody (ADA) assessment. Patients will be grouped according to treatment received or, if no treatment is received prior to study discontinuation, according to treatment assigned.

The numbers and proportions of ADA-positive patients and ADA-negative patients at baseline (baseline prevalence) and after etrolizumab treatment (post-treatment incidence) will be summarized by treatment group. When determining post treatment incidence, patients are considered to be ADA positive if they are ADA negative or have missing data at baseline but developed an ADA response following study drug exposure (treatment-induced ADA response), or if they are ADA positive at baseline and the titer of one or more postbaseline samples is at least 0.60 titer unit greater than the titer of the baseline sample (treatment-enhanced ADA response). Patients are considered to be ADA negative if they are ADA negative or have missing data at baseline and all postbaseline samples are negative, or if they are ADA positive at baseline but do not have any postbaseline samples with a titer that is at least 0.60 titer unit greater than the titer of the baseline sample (treatment unaffected).

The relationship between ADA status and safety, efficacy, PK, and PD endpoints will be assessed and reported via descriptive statistics.

### **Biomarker Analyses**

Beta 7 receptor occupancy and serum MAdCAM-1 results will be summarized by dosing group and timepoints as absolute values and/or change from baseline. Summary statistics may be provided.

A PK/PD model may be developed to evaluate the PK/PD relationship after combining data from adult's study. This modeling work will be reported separately outside the Clinical Study Report of this study.

### **Exploratory Analyses**

PUCAI/PCDAI response or remission rates will be summarized descriptively over time within each treatment group. Disease activity scores and subscores, fecal calprotectin levels and serum C-reactive protein (CRP) levels and their change from baseline will also be summarized descriptively over time to assess the efficacy of etrolizumab in reducing signs and symptoms of disease and levels of inflammatory biomarkers.

